7.2 Methods for Data Processing

7.2.1 Early withdrawal and missing data

No missing data will be imputed unless otherwise specified. In case of missing categorical data, it will be listed as a missing item. Missing dates for concomitant medications and adverse events (AEs) will be imputed.

Missing dates for concomitant medications will be imputed as follows. Missing dates for

concomitant medications will be imputed only to judge the classification (prior/concomitant), and the list still shows unimputed dates.

- Starting date of concomitant medication is missing
 - 1) If the year and month are known, the missing day will be imputed as the first day of the corresponding month.
 - If only the year is known, the missing month and day will be imputed as January
 1.
- The end date of concomitant medications is missing
 - 1) If the year and month are known, the missing day will be imputed as the last day of the corresponding month.
 - 2) If only the year is known, the missing month and day will be imputed as 31 December.

The imputed start date of the concomitant medication should not be earlier than the subject's date of birth, and the imputed end date should not be later than the subject's date of death. The imputed start date of the concomitant medication should be earlier than or equal to the end date of the concomitant medication.

Missing dates of AEs are imputed as follows: missing dates of AE are imputed for the purpose of AE classification only, and unimputed dates are still displayed when AE-related data listings will be generated.

- Missing of start date of AE
 - 1) If the year and month are known and both are earlier than those of the first dose of the investigational drug, the last day of the known month will be used for imputation.
 - 2) If the year and month are known and equal to the year and month of the first administration of the investigational drug, and the end date is missing or equal to or later than the date of the first administration of the investigational drug, the start date of the AE should be equal to the date of the first administration of the investigational drug [date means "xx xx (month day)"]; if the end date is earlier than the date of first administration of the investigational drug, the first administration of the investigational drug the first administration of the investigational drug the first administration of the investigational drug, the first day of the known month will be used for imputation.
 - 3) If the year and month are known and later than those of the first dose of the investigational drug, it will be imputed with the first day of the known month.
 - 4) If only the year is known and earlier than that of the first dose of the investigational drug, "December 31" will be used for imputation.
 - 5) If only the year is known and same as that of the first dose of the investigational

drug, and the end date is missing or the same as or later than the date of the first dose, the start date of AE is the date of the first dose of the investigational drug (date refers to "month, day").

- 6) If only the year is known and later than that of the first dose of the investigational drug, it will be imputed with "January 1".
- 7) If the year, month, and day are all missing, and the end date is missing or equal to or later than the date of first administration of the investigational drug, the date of first administration of the investigational drug will be used as the corresponding start date.
- 8) Other conditions are regarded as missing.
- Missing of end date of AE
 - 1) If the year and month are known, it will be imputed with the last day of the known month.
 - 2) If only the year is known, it will be imputed with "December 31".
 - 3) Other conditions are regarded as missing.

The imputed AE start date should not be earlier than the subject's date of birth, and the imputed AE end date should not be later than the subject's date of death. The imputed AE end date should be later than or equal to the AE start date.

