4.2.2 Adverse Events

Adverse Events

An adverse event (AE) is any untoward medical occurrence (e.g., any unfavorable and unintended sign [including abnormal laboratory findings], symptom or disease) in a clinical investigation participant after providing written informed consent for participation in the study. Therefore, an AE may or may not be temporally or causally associated with the use of a medicinal (investigational) product. Abnormal laboratory values or test results constitute AEs only if they fulfill at least one of the following criteria:

- they induce clinical symptoms or signs;
- they are considered clinically significant
- they require therapy

Treatment Emergent Adverse Event

A treatment emergent adverse event (TEAE) is an adverse event that occurs from the first dose of the study drug to 30 days after the last study treatment, or events occurring before the start of the treatment period and meeting any of the following three changes, as determined by the same preferred term (PT) under the same system organ class (SOC) based on MedDRA coding.

- (1) Events which are present prior to the start of the treatment period but increased in severity;
- (2) Events that change from being not suspected to being suspected of study drug relationship;
- (3) Events that develop into SAEs after the start of the treatment period.

The increase in severity described above means that the same PT under the same SOC is present before the first administration of the investigational drug, but the severity of the PT during treatment is higher than the most severe grade before administration, or a new adverse event that occurs during treatment has a more severe grade (the same PT under the same SOC).

Severity is graded as mild, moderate and severe:

- Mild: usually transient in nature and generally not interfering with normal activities.
- Moderate: sufficiently discomforting to interfere with normal activities.
- Severe: prevents normal activities.

Treatment emergent adverse events will be counted for the specific treatment period. TEAEs in the ACEI/ARB treatment group refers to the adverse events that occur after the subject's

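### The SAP imputes partial AE start dates against one undefined first-dose date and has no rule at the ARNI switch, so events can be counted in the wrong treatment period

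*SAP*

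**What the plan says.** SAP 4.2.2: "Treatment emergent adverse events will be counted for the specific treatment period". An ACEI/ARB event starts after the first ACEI/ARB dose and before ARNI. An ARNI event starts from the first ARNI dose up to 30 days after the last one.

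SAP 7.2.1 says that "missing dates of AE are imputed for the purpose of AE classification only"; listings keep the unimputed dates. The start-date rules that matter here are:

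- Rule 2, day missing, month of the first dose: "the start date of the AE should be equal to the date of the first administration of the investigational drug", if the end date is missing or not before that dose.
- Rule 3, day missing, month after that of the first dose: "it will be imputed with the first day of the known month".
- Rule 5, only the year known, same year as the first dose: "the start date of AE is the date of the first dose of the investigational drug", under the same end-date condition.
- Rule 6, "If only the year is known and later than that of the first dose of the investigational drug": 1 January.
- Rule 7, date wholly missing: "the date of first administration of the investigational drug will be used as the corresponding start date", again subject to the end-date condition.
- Rule 8, anything else: left missing.

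No rule refers to the first ARNI dose as a separate date.

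**The concern.** The imputed start date has one purpose, to classify the event, and in this design that includes choosing the treatment period. A rule with one anchor can separate events before and after that anchor. It cannot handle a second boundary six months away. A partial date that spans the boundary is resolved the same way every time, so the errors do not cancel.

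The study is single-arm and sequential, so the by-period AE tables are its only safety comparison of ARNI with ACEI/ARB. If the anchor is the first ACEI/ARB dose, the errors lower the ARNI count and raise the comparator count, which favours the test drug.

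**Working it through.** **Which dose is the reference?** The SAP does not define the investigational drug, and the two documents point in different directions.

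- SAP 4.2.2 ends the pre-treatment period at the first dose of the investigational drug. If that meant ARNI, every event on ACEI/ARB would be pre-treatment, which contradicts the ACEI/ARB definition in the same section.
- SAP 7.3.5 defines prior medication by the first dose of study drug and concomitant medication by the first dose of the investigational drug. The two categories are complementary only if these are the same date.
- The protocol glossary defines the investigational drug as the drug under test, and protocol Table 6-1 lists ACEI and ARB as control drugs. That meaning is ARNI.

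SAP usage therefore favours the first ACEI/ARB dose, but does not settle it. Both readings were checked.

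**Inputs.** From the documents: six months per treatment (protocol 12.3), the 30-day tail (SAP 4.2.2) and rules 1 to 8 (SAP 7.2.1). Assumed: first ACEI/ARB doses spread evenly over a 365-day calendar year, ARNI starting 183 days later, onset equally likely on every day, and an end date either missing or seven days after onset. Every combination of start day and onset day was enumerated. The ARNI period has 365 − 183 = 182 days, or 182 + 30 = 212 with the tail.

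**Reference = first ACEI/ARB dose**

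*Day missing.* Rule 3 sets day 1 of the month. That precedes the switch only in the switch month, and only if ARNI did not start on the 1st. Averaged over start dates, 5,373 / 365 = 14.7 ARNI days per patient are affected: 14.7 / 182 = 8.1%, or 14.7 / 212 = 6.9% with the tail. Later months are placed correctly.

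*Year only.* For 182 start dates, ARNI begins in the next calendar year after 1 January. Rule 6 then puts events from that year on 1 January, before the switch. For another 182, ARNI begins in the first-dose year, and rule 5 moves the ARNI days left in that year (1 + 2 + … + 182 = 16,653 in total) to the first dose. In the one remaining case ARNI starts on 1 January and nothing moves.

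- 12 months: (182 × 182 + 16,653) / (365 × 182) = 49,777 / 66,430 = 74.9%.
- With the tail: (182 × 212 + 16,653 − 435) / (365 × 212) = 54,802 / 77,380 = 70.8%. The 435 are tail days falling in a third calendar year, which rule 6 places correctly.

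*Wholly missing.* Rule 7 sends every ARNI event to the first ACEI/ARB dose, because its end date is missing or later: 100%.

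*Reverse error.* 0% in each case. For an on-treatment event the imputed date is never later than the true onset.

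**Both readings side by side**

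| Incomplete date | Reference ACEI/ARB: ARNI events moved to ACEI/ARB | Reference ARNI: ACEI/ARB events moved to ARNI, end date missing | Reference ARNI: same, end date = onset + 7 days |
|---|---|---|---|
| Day missing | 6.9–8.1% | 8.0% | 3.3% |
| Year only | 70.8–74.9% | 74.8% | 3.8% |
| Wholly missing | 100% | 100% | 3.8% |

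With ARNI as the reference, no ARNI event moves to ACEI/ARB. With a seven-day end date, however, 71.0% of year-only and 96.2% of wholly missing ACEI/ARB dates fall to rule 8 and stay missing.

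**The case against.** The strongest objection is that the direction rests on an undefined term. On the protocol's meaning, every error runs towards ARNI and rule 3 misplaces nothing. This stands, so the direction can only be stated conditionally. It does not rescue the rule: either way a single anchor serves two periods and the errors run one way.

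A reader might also infer that ARNI events with incomplete dates generally move to ACEI/ARB. The documents do not support that. When the month is known, about 92–93% of ARNI events stay in ARNI. The large shifts need a year-only or wholly missing date, and the plan works against those: AE start and end dates are to be reported as far as possible (protocol 10.1.1), AEs are sought at every visit, including months 6 and 7 around the switch (protocol Table 8-1), and missing values are queried (protocol 11.2). Such dates should be rare, although no count is given.

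Nor do the documents show that ARNI safety will be materially understated. The percentages apply only to events with incomplete dates. Safety has no formal inference (protocol 12.5.3), and the listings show the unimputed dates, so affected events can be found.

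Finally, a second anchor does not remove the error; it changes its direction. That is correct and belongs in the SAP text.

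**Conclusion.** The point holds as a minor defect. SAP 7.2.1 uses one undefined reference date to classify events that SAP 4.2.2 splits between two periods, and its rules misallocate some of them in one direction. With the first ACEI/ARB dose as reference, the better-supported reading, the direction is ARNI to ACEI/ARB: about 7–8% of day-missing ARNI events (all in the switch month), 71–75% of year-only events and 100% of wholly missing dates, with none in reverse. With ARNI as reference, the direction reverses. The sizes assume uniform entry and onset and a switch at day 183; the lower end of each range includes the 30-day tail. The effect on any AE table cannot be sized, because the number of incomplete dates is not given.

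**What to change.** Make two changes in SAP 7.2.1.

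1. Define the reference for the existing rules as the first dose of any study treatment.
2. Add a second anchor. If the partial start date is compatible with the ARNI period and the end date is missing or not before the first ARNI dose, set the start to the later of the imputed date and the first ARNI dose date. This extends to the switch the convention that rules 2, 5 and 7 already use at the first dose.

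The SAP should state the downside. Under the same assumptions no ARNI event then moves to ACEI/ARB, but ACEI/ARB events move to ARNI: 8.0% (day missing), 74.8% (year only) and 100% (wholly missing) when the end date is also missing, and 3.3%, 3.8% and 3.8% when an end date seven days after onset is recorded. With that end date and the reference defined as in step 1, the remaining ACEI/ARB events stay in ACEI/ARB and are not left missing. The residual error counts against the test drug, which is the usual preference for a safety table, but it is a preference.

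The cost is one definition, one rule and a small programming change. Listings are unaffected because they show unimputed dates. Reporting the number of AEs with imputed start dates, by period and type of missing date, would let readers see how little or how much depends on the rule.

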7.2.2 Derived and converted data

Except for the calculation of certain study endpoints based on the data collected from CRF, no other data are derived or converted. For outliers, data queries are reported to the DM and solved or verified before database lock. No special data processing is performed.

7.3 Study Subjects

7.3.1 Subject disposition

The number of subjects who had signed the informed consent form but not enrolled are calculated, making the distinction between screen failures and subjects who do not fail screening but are not enrolled. Screen failures and subjects who did not fail screening but are not enrolled are listed, providing the reasons.

Based on safety analysis set, the number and percentage of subjects who had completed and early withdrawn from the study are calculated, as well as the number and percentage of subjects who early withdrew due to various reasons. Reasons for early withdrawal are listed.

7.3.2 Protocol deviations

Based on the safety analysis set, details of subjects with major protocol deviations should be listed.

7.3.3 Analysis datasets

Based on the safety analysis set, the number and percentage of subjects included in the efficacy analysis set and per protocol set will be calculated. Reasons for non-inclusion are listed.

7.3.4 Demographics and baseline characteristics

The analysis is performed based on the SS.

The age, sex, ethnicity, height, weight, BMI, and other demographic data are statistically described. Past medical history, history of present illness, history of heart failure and NYHA classification will be statistically described.

Demographic data, past medical history, history of present illness, history of heart failure, and NYHA classification will be listed.

7.3.5 Prior and concomitant medications and therapies

The analysis is performed based on the SS.

The duration of non-investigational drug use will be compared with the duration of study drug use, and non-investigational drug use will be divided into prior and concomitant medications.

Prior medication refers to a non-investigational drug that is started and ended before the first dose of study drug. Concomitant medication refers to a non-investigational drug that meets one of the following conditions:

- 1) Starting at or after the first dose of the investigational drug
- 2) Starting before the first dose of the investigational drug and continuing at or after the first dose of the investigational drug.

The number and percentage of subjects using various drugs will be calculated for prior and concomitant medications respectively. The prior and concomitant medications will be listed.

Concomitant treatments (including all non-drug concomitant treatments such as surgery) will be listed.

7.3.6 Treatment compliance

The analysis is performed based on the SS.

The study drug compliance will be described statistically as a quantitative variable.

7.4 Efficacy Analysis

7.4.1 Efficacy analysis of primary endpoint

The analysis will be based on the efficacy analysis set and the per protocol set.

- Proportion of paired patients who developed at least one SVT over 6 months of ACEI/ARB and 6 months of ARNI treatment.
- Paired proportion of patients by the occurrence of at least one NSVT over 6 months of ACEI/ARB and 6 months of ARNI treatment.
- Paired proportion of patients by the occurrence of at least one PVC over 6 months of ACEI/ARB and 6 months of ARNI treatment.
- Paired proportion of patients by the occurrence of at least one ICD or CRT-D shock over 6 months of ACEI/ARB and 6 months of ARNI treatment.
- Paired proportion of patients by the occurrence of at least one ATP event over 6 months of ACEI/ARB and 6 months of ARNI treatment.

Different hypothesis testing will be done on different types of variables:

Analysis of paired patient proportion

Occurrence events to be considered are SVT, NSVT, PVC, ICD or CRT-D shocks and ATP.

For each of the occurrence event, number of patients with at least one event stratified by treatments, will be presented in a 2×2 contingency table as follow:

ARNI (case)	ACEI/ARB (control)		
	At least one event	No event	Total
At least one event	a	b	a + b
No event	С	d	c + d
Total	a + c	b + d	N = a + b + c + d

Table 5-1 Matched pairs 2 × 2 contingency table

The following statistical hypothesis under 95% significance level will be tested to address the primary objective:

Null hypothesis: $p_b = p_c$ versus alternative hypothesis: $p_b \neq p_c$, where p_b and p_c are b/N and c/N, respectively. The test statistic considered is McNemar Test statistic as follow:

$$\chi^2 = \frac{\left(b-c\right)^2}{b+c}$$

which has a chi-squared distribution with degree of freedom of one.

However, an exact test (binomial sign test) will be used if the discordant cells have low values (b + c < 25).

Supportive analyses

In addition to the primary analysis, all the paired proportion will also be analyzed using the Liddell's exact test (Liddell 1983) as supportive analysis. From Table 5-1, the maximum likelihood estimate of relative risk (Mantel and Haenszel 1959), \hat{R} is given as follow:

$$\widehat{R} = \frac{b}{c}$$

Null hypothesis: $\hat{R} = 1$ versus alternative hypothesis: $\hat{R} \neq 1$ The test statistic considered, *F* is given as follow:

$$F = \frac{b}{c+1}$$

which has a F-distribution with degrees of freedom of 2(c+1) and 2b. Two-sided probability and 95% confidence interval of estimated relative risk will be presented as well.

For all primary endpoints, the proportion of patients with at least one event over 3 months of ACEI/ARB and 3 months of ARNI treatment will be analyzed.

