6.7 Preparation and dispensation

Each study site will be supplied with ARNI in packaging as described under investigational section. Storage must obey instructional request.

Authorized investigator and drug administrator are responsible for dispensing drug at visit 4, 5, 6 and recycling at visit 5, 6, 7. The number of ARNI distributed was calculated according to the investigator's order and the window period of treatment, and was distributed in the smallest unit, namely box. If titration adjustment is happened between two continuous visits, enough ARNI dose should take into investigator's consideration to avoid drug shorting, or investigators are responsible for reminding patient to go to site and receipt supplementary ARNI in time.

Patients must take medicine follow by doctor advice, return ARNI pack and the redundant drug. After returning back drugs at visits, authorized investigator and drug administrator are needed to check the drug tablet accord with their diary card and assess patient compliance.

In case the ARNI dosage is not enough for monthly titration modification, the investigator is obligated to remind the patients to return the site and dispense ARNI.

ACEI/ARB is prescribed by the investigators according to the clinical routine.

During the COVID-19 pandemic in which on-site study visits may be impacted, delivery of study treatment directly to a patient's home is generally permitted. If delivery is not available, patients may purchase the study drugs themselves. Patients will be reimbursed for the study drug cost with drug packaging as proof of purchase.

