Information about common side effects already known about the investigational drug can be found in the label. This information will be included in the patient informed consent and should be discussed with the patient during the study as needed. Any new information regarding the safety profile of the investigational drug that is identified between label updates will be communicated as appropriate, for example, via an investigator notification (IN) or an aggregate safety finding. New information might require an update to the informed consent and then must be discussed with the patient. In the event of recollection of informed consent is needed, the Investigator may conduct the informed consent discussion remotely (e.g., telephone or video conference). Guidance issued by local regulatory bodies, and ECs/IRBs on this aspect prevail and must be implemented and appropriately documented (e.g., the presence of an impartial witness, sign/dating separate ICFs by trial participant and person obtaining informed consent, etc.).

Women of childbearing potential must be informed that taking the study treatment may involve risks to the fetus if pregnancy were to occur during the study and agree that in order to participate in the study they must adhere to the contraception requirements.

Male patients must be informed that if a female partner becomes pregnant while he is enrolled in the study, contact with the female partner will be attempted to request her consent to collect pregnancy outcome information.

8 Visit schedule and assessments

The Assessment Schedule (Table 8-1) lists all of the assessments when they are performed. All data obtained from these assessments must be supported in the patient's source documentation.

Patients should be seen for all visits/assessments as outlined in the assessment schedule (Table 8-1) or as close to the designated day/time as possible. Missed or rescheduled visits should not lead to automatic discontinuation.

Patients who discontinue from the study treatment are to complete the end of treatment visit as soon as possible, and attend the follow-up visits as indicated in Table 8-1.

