12.8 Sample size calculation

12.8.1 Primary endpoint

McNemar Test is used in the primary analysis to test for 2 correlated proportions. Approximate formula from Machin et al (1997) is used to calculate the minimum size required.

For the proportion of discordant pairs, the following approximate formula is used:

Proportion Discordant =
$$P_t(1 - P_s) + P_s(1 - P_t)$$

where P_t and P_s are proportion of patients experiencing the event of interest during ACEI/ARB and ARNI treatment period respectively. Over here, both proportions are assumed to be similar to de Diego et al (2018)'s study. According to de Diego et al (2018)'s study, SVT (one of the VA event) has the following incidence 8/120 and 1/120 during ACEI/ARB and ARNI treatment period respectively. Hence, by substitute both into the equation above, proportion discordant calculated is 0.0739 after rounding off.

For the difference, a parameter under effect size is approximated by the following formula:

Effect Size =
$$P_t(1 - P_s) - P_s(1 - P_t)$$

and after substituting P_t and P_s defined above, the effect size calculated is -0.0583.

Thus, by considering the parameters defined above, power of 0.8 and significance level of 0.05, the sample size required is 175. Further consider a dropout rate of 20%, the minimum sample size required is 219.

The above calculation is calculated using PASS 11 software's Test for Two Correlated Proportion (McNemar Test) [Differences] procedure.

For proportion of patients had ICD or CRT-D shocks occurrence over 6 months of ACEI/ARB and 6 months of ARNI treatment, the above sample size will provide 95% - 98% power to detect a proportion difference of 0.075 at two-sided significance level of 0.05. The proportion difference is derived from the published literature (de Diego et al 2018).

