3.2 Sample Size Calculation

3.2.1 Primary endpoint

McNemar Test is used in the primary analysis to test for 2 correlated proportions. Approximate formula from Machin et al (1997) is used to calculate the minimum size required.

For the proportion of discordant pairs, the following approximate formula is used:

Proportion Discordant = $P_t (1 - P_s) + P_s (1 - P_t)$

where P_t and P_s are proportion of patients experiencing the event of interest during ACEI/ARB and ARNI treatment period respectively. Over here, both proportions are assumed to be similar to de Diego et al (2018)'s study. According to de Diego et al (2018)'s study, SVT (one of the VA event) has the following incidence 8/120 and 1/120 during ACEI/ARB and ARNI treatment period respectively. Hence, by substitute both into the equation above, proportion discordant calculated is 0.0739 after rounding off.

For the difference, a parameter under effect size is approximated by the following formula:

Effect Size =
$$P_t (1 - P_s) + P_s (1 - P_t)$$

 P_t and P_s after substituting Pt and Ps defined above, the effect size calculated is 0.0583.

Thus, by considering the parameters defined above, power of 0.8 and significance level of 0.05, the sample size required is 175. Further consider a dropout rate of 20%, the minimum sample size required is 219.

The above calculation is calculated using PASS 11 software's Test for Two Correlated Proportion (McNemar Test) [Differences] procedure.

For proportion of patients had ICD or CRT-D shocks occurrence over 6 months of ACEI/ARB and 6 months of ARNI treatment, the above sample size will provide 95% - 98% power to detect a proportion difference of 0.075 at two-sided significance level of 0.05. The proportion difference is derived from the published literature (de Diego et al 2018).

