7.1 Overall Statistical Considerations

All statistical analyses are performed using SAS9.4.

All subjects related, efficacy related and safety related data should be collected and included in the statistical analysis. Notes or descriptive text records are only listed. For other data, descriptive statistical analysis would be performed, also statistical inference would be applied if needed.

In the statistical tabulations, screening number of subjects is the universal unique identifier of subjects in the study.

General rules of descriptive statistics: Quantitative variables are described by mean, standard deviation, standard error, median, minimum, maximum, Q1 and Q3. Categorical variables are

described by number and percentage of each category. Two-sided 95% confidence intervals will also be calculated for efficacy endpoints.

In the laboratory test part and the efficacy analysis part, 2 digits will be retained for the upper and lower limits of means and their confidence intervals, 3 digits for standard deviations, and 2 digits for medians, minimums, maximums, Q1 and Q3. In other parts, 1 digit more than the original values can be retained for the upper and lower limits of means and their confidence intervals, 2 digits more for standard deviations, and the original value digits for medians, minimums, maximums, Q1 and Q3. One decimal place will be retained for percentages and the upper and lower limits of their confidence intervals (but for efficacy analysis, 2 decimal places will be retained).

General principles of statistical inference: paired t test and Wilcoxon rank sum test will be used to compare quantitative data. McNemar test, exact test (binomial sign test) and Liddell's exact test will be used to compare categorical variables. All statistical tests will be subjected to twosided tests (unless otherwise specified), and a P-value less than or equal to 0.05 will be considered to indicate a statistically significant difference (unless otherwise specified).

For values such as "< xxx", half of the number following the less-than sign will be used to summarize and calculate statistics. For values such as "> xxx", xxx will be used to summarize and calculate statistics. For values such as "xx-xx", the average of the numbers before and after "-" will be used to summarize and calculate statistics. P value is rounded to 4 decimal places. If P < 0.0001, it is presented as '< .0001'; if P > 0.9999, it is presented as '> .9999'.

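### The primary any-event comparison does not define the two observation windows, so a patient's ARNI window can be shorter than the ACEI/ARB window with no correction

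*SAP*

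**What the plan says.** Each primary endpoint classifies a patient as having at least one event, or none, in each treatment period. The SAP's NSVT item reads "Paired proportion of patients by the occurrence of at least one NSVT over 6 months of ACEI/ARB and 6 months of ARNI treatment". SVT, PVC, shocks and ATP are handled the same way (Protocol 12.4.1, SAP 7.4.1). The test is McNemar's, or the exact sign test when there are fewer than 25 discordant pairs.

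Protocol Table 8-1 counts all visits from month 0: Visit 4 at 6 months ± 2 weeks and Visit 7 at 12 months ± 2 weeks. Protocol 6.7 makes site staff "responsible for dispensing drug at visit 4, 5, 6 and recycling at visit 5, 6, 7", so ARNI cannot start before Visit 4. SAP 7.1 takes Visit 4 as the ARNI baseline. Protocol section 8 adds: "Missed or rescheduled visits should not lead to automatic discontinuation".

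The text of Protocol sections 3 and 6.1.5 and SAP section 3 promises six months for each treatment. Nothing re-times Visits 5 to 7 from the actual ARNI start.

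The SAP's efficacy analysis set (section 6) includes patients who withdraw early after at least one ARNI dose. Protocol 12.4.4 calls for a complete-case analysis without saying when a period is complete. Protocol 12.4.5 plans no sensitivity analysis. Per-day standardisation appears only in SAP 7.4.2, for changes in the secondary count and duration variables.

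**The concern.** The chance of at least one event rises with the time observed. If the ACEI/ARB window is on average longer than the ARNI window, fewer patients will be positive on ARNI even when the drug does nothing.

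There are two routes to that. One is a Visit 4 that tends to run late while Visit 7 does not follow. The other is withdrawal after ARNI has started. The second is one-sided by construction: a member of the efficacy set has already passed through ACEI/ARB, so only the ARNI window can be cut short. Protocol 9.1.1 makes it practical, because the minimum data after treatment discontinuation are concomitant treatments and adverse events, not device data.

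Per-day scaling cannot repair a yes/no outcome, so the primary test needs a window rule of its own. SAP 7.4.1 also adds a 3-month version of the endpoint, again without one.

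**Working it through.** **The plan's own figure.** The SAP takes SVT "incidence 8/120 and 1/120 during ACEI/ARB and ARNI treatment period respectively".
- Discordant proportion: 0.0667 × 0.9917 + 0.0083 × 0.9333 = 0.0739, which matches "proportion discordant calculated is 0.0739 after rounding off".
- Difference: 0.0667 − 0.0083 = 0.0583, the magnitude in "the effect size calculated is -0.0583".
- The SAP states "power of 0.8 and significance level of 0.05, the sample size required is 175". The exact two-sided test first reaches 80% at n = 175 (80.2%). The normal approximation gives 169.
- 175/0.80 = 218.75, rounded up to 219. The sample size is not in question.

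**Window lengths** (6 months = 26 weeks). ACEI/ARB: 26 ± 2 = 24 to 28 weeks. ARNI: (52 ± 2) − (26 ± 2) = 22 to 30 weeks.

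**Model with no drug effect.** Let I be the 6-month incidence, with a constant rate h = −ln(1 − I)/26. The event probability in w weeks is 1 − exp(−hw). At I = 50%, 28 weeks gives 1 − 0.5^(28/26) = 52.6% and 24 weeks gives 1 − 0.5^(24/26) = 47.3%, a spurious difference of about 5.3 points. For SVT (6.7%) the values are 7.2% and 6.2%, about 1 point against a design difference of 5.8.

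I computed the exact rejection probability of the planned rule at N = 175. SAP 7.1 sets the sidedness: "All statistical tests will be subjected to twosided tests (unless otherwise specified"). Three models were run: no between-patient variation, and gamma frailty of shape 1 and of shape 0.5, with S(w) = (1 + θw)^(−k) and θ = [(1 − I)^(−1/k) − 1]/26. Ranges below span the three. Only the SVT incidence comes from the documents; 30%, 50% and 70% are assumptions.

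| Scenario, % rejecting | SVT 6.7% | 30% | 50% | 70% |
|---|---|---|---|---|
| 26 v 26 weeks | 3.1–3.5 | 4.9–5.1 | 4.9–5.0 | 4.7–5.1 |
| Visits 4 and 7 both even over ± 2 weeks | 3.1–3.5 | 4.9–5.1 | 4.9–5.0 | 4.7–5.1 |
| Visits 4 and 7 both 0–2 weeks late | 3.2–3.7 | 5.3–5.5 | 5.3–5.7 | 5.0–6.0 |
| Visit 4 0–2 weeks late, Visit 7 even over ± 2 | 3.4–3.8 | 6.4–6.9 | 6.7–8.0 | 6.1–9.0 |
| Every patient at 28 v 24 | 4.3–4.8 | 10.8–12.4 | 11.9–17.0 | 10.0–20.6 |

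At 28 v 24 and 50% without frailty, 16.8 of the 17.0 points favour ARNI. Reversing the windows (24 v 28) gives the same rate against ARNI.

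**Truncated ARNI follow-up, visits on time.** Let a fraction f of patients have ARNI observation end at a uniformly distributed time unrelated to arrhythmia, and count as complete. At I = 50% without frailty, a truncated patient has ARNI event probability 1 − 0.5/ln 2 = 27.9%.
- f = 10%: 0.9 × 50% + 0.1 × 27.9% = 47.8% on ARNI against 50% on ACEI/ARB; rejection 7.0–7.1% over the three models.
- f = 20%: 0.8 × 50% + 0.2 × 27.9% = 45.6%; rejection 13.2–13.9%.

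**Equal windows.** With both periods cut to 24 weeks, rejection without frailty returns to 3.3% for SVT and 5.0% at 50%. On the SVT design inputs, power at N = 175 is 76.0% with 24-week windows and 71.0% with 22-week windows.

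**The case against.** The plan can be read more kindly. Visit 7 has its own two-week tolerance and can absorb a two-week delay at Visit 4. The text repeatedly promises six months per drug, and the endpoint itself names six months of each, which taken literally means equal windows. The complete-case rule might exclude truncated patients. The documents contain no visit-timing data. The tolerance for rescheduling covers every visit, and the COVID-19 text in Protocol 6.7 mainly concerns drug delivery. The same pressures could delay Visit 7, which lengthens the ARNI window. For SVT, the event the trial was sized on, no within-window scenario tabulated above exceeds 5%.

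All of that limits size and direction. None of it supplies the missing rule: nothing obliges Visit 7 to follow Visit 4, six months is not defined in days from first dose, and completeness is left open.

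A reader might go further and infer that Visit 7 is fixed, that each week of delay at Visit 4 is a week credited to ARNI, and that the error rate is 17% or more. The documents do not support that. It needs every patient at the limit of the Visit 4 window, Visit 7 never moving, and an incidence near 50% that no document gives. Nor does the full shift carry over to the 3-month contrast: if it runs over Visits 1 to 3 and 4 to 6, a delay of d weeks at Visit 4 shortens only the ARNI side, so the gap is d rather than 2d.

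A practical objection also stands. Dated episodes cannot be taken for granted for PVC, which is analysed as an hourly number and may come from 24-hour Holter recordings at three visits.

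**Conclusion.** The point holds as a gap in the analysis definition. The two windows can differ within a patient, the primary test makes no allowance for it, and the status of a truncated ARNI period is undefined.

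Symmetric visit variation does no harm. A net bias towards ARNI needs either Visit 4 lateness not matched at Visit 7 or truncated ARNI follow-up counted as complete. On the stated assumptions (no drug effect, constant rate, N = 175) the false-positive rate is then about 6 to 9% for plausible lateness at incidences of 30 to 70%, and about 7 to 14% for 10 to 20% truncation at 50% incidence. The extreme of 28 v 24 weeks for everyone gives 10 to 21%, and at most 4.8% for SVT. The incidences, the lateness and the truncation fractions are assumptions. The consequence is therefore moderate and depends on how common NSVT, PVC, shocks and ATP prove to be. The remedy is simple enough that it should be made.

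**What to change.** In SAP 7.4.1:
- Start each window at the first study dose of that drug, and reconcile Table 8-1 with the promise of six months for each treatment.
- State whether a truncated period counts as complete under Protocol 12.4.4. This matters for the equal-window rule too: a patient who leaves a week after starting ARNI would otherwise contribute one week per drug.
- For dated device episodes (SVT, NSVT, shocks, ATP), count events over the same number of days on each drug within a patient: the shorter of the two windows, at most 182 days, or 91 for the 3-month contrast. Make this the primary rule, or at least a pre-specified sensitivity analysis. Apply it to PVC only if the device data carry dates.
- Tabulate both window lengths.

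The cost is SAP wording, a date filter and a check that device reports date each episode. Some events in the longer window go unused. On the SVT inputs power falls from 80% to about 76% if every patient is cut to 24 weeks, and to 71% at 22 weeks. Restoring 80% would take 189 evaluable patients (237 enrolled) or 206 (258). If that loss is unwelcome, the sensitivity-analysis option leaves the primary power untouched and still shows whether window length drives the result.
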